Appendix 4. Hepatic Monitoring Tests for Treatment-Emergent Abnormality

Selected tests may be obtained in the event of a treatment-emergent hepatic abnormality and may be required in follow-up with patients in consultation with Lilly or its designee CRP.

Hepatic Monitoring Tests

Hepatic Hematology^a

Hemoglobin
Hematocrit
RBC
WBC
Neutrophils
Lymphocytes
Monocytes
Eosinophils
Basophils
Platelets

Hepatic Chemistry^a

Total bilirubin
Conjugated bilirubin
Alkaline phosphatase
ALT
AST
GGT
CPK

Haptoglobin^a

Hepatic Coagulation^a

Prothrombin Time
Prothrombin Time, INR

Hepatic Serologies^{a,b}

Hepatitis A antibody, total
Hepatitis A antibody, IgM
Hepatitis B surface antigen
Hepatitis B surface antibody
Hepatitis B Core antibody
Hepatitis C antibody
Hepatitis E antibody, IgG
Hepatitis E antibody, IgM

Anti-nuclear antibody^a

Alkaline Phosphatase Isoenzymes^a

Anti-smooth muscle antibody (or anti-actin antibody)^a

Abbreviations: ALT = alanine aminotransferase; AST = aspartate aminotransferase; CPK = creatinine phosphokinase; GGT = gamma-glutamyl transferase; Ig = immunoglobulin; INR = international normalized ratio; RBC = red blood cells; WBC = white blood cells.

^a Assayed by Lilly-designated or local laboratory.

^b Reflex/confirmation dependent on regulatory requirements and/or testing availability

- Clarify that patients may consume up to 20 g of carbohydrates to treat or prevent hypoglycemia (regardless of hypoglycemia level) during fasting periods.

Revised Protocol Sections

| |
|---|
| 
Note: All deletions have been identified by strikethroughs. All additions have been identified by the use of underline.
 |
|---|

Study Schedule Protocol I8B-MC-ITRV

| Procedure | Sign Informed Consent | Screening | Lead-in | Study Period (Periods 1 to 4) | | Follow-up/Early discontinuation | Comments |
|---|-----------------------|-----------|-------------------------|-------------------------------|--------------------------------------|---------------------------------|---|
| | | | | Day -1 | Day 1 | | |
| | | | | | | | |
| Vital signs(semi-recumbent): blood pressure and pulse rate | | X | 14 days prior to Day -2 | | Predose, 30 and 120 minutes postdose | X | Vital signs will be taken while patients are supine at screening and semi-supine on Day 1. |
| 12-lead ECG | | X | | | Predose (Period 1) | X | Single ECGs will be collected for safety. |
| Clinical laboratory tests | | X | | | Predose for Period 1 only | X | Fasting laboratory test for screening and follow-up . Screening laboratory tests will be analyzed at a local laboratory (see Section 9.5.2). Follow up screening not fasted. |
| | | | | | | | |
| Pregnancy test | | X | | X | | X | For female patients of childbearing potential only. Serum pregnancy test will be performed at screening and urine pregnancy tests will be performed at admission for Period 1 and at follow-up (see Appendix 2) |

3.2 Background

...

LY900014 represents a new formulation that contains insulin lispro, treprostinil, citrate and other excipients. This formulation involves the novel use of a microdose of treprostinil (Remodulin[®]) as an excipient to enhance the absorption of insulin lispro by local vasodilatation rather than as an active pharmaceutical ingredient to elicit a systemic effect. Treprostinil is a prostacyclin analogue, administered either through inhalation (Tyvaso[®]), as an intravenous (IV) infusion or as a continuous SC administration for the treatment of symptomatic pulmonary arterial hypertension (PAH) and has been approved in the US since 2002 and in Germany since 2006 (AMIS database [WWW] Remodulin package insert, 2014).

6.3.1 Meals and Dietary Restrictions

Patients will be fasted (except for water) for at least 10 hours before each test meal and 8 hours prior to screening and follow-up assessments (see Section 9.5.8 for guidelines on hypoglycemia treatment). The patient will not be allowed to consume water for 2 hours after the MMTT assessment begins; however, water may be consumed freely 2 hours postmeal.

9.2.2 Dose-Finding Assessment

After transitioning to a stable dose of insulin glargine, patients may return to the CRU on Period 1, Day -1 in the early morning for the dose-finding assessment, which may begin between 07:00 and 11:00.

...

Following completion of procedures associated with the dose finding assessment, patients may be offered a meal. Patients will have the option to remain inpatient at the CRU until the Study MMTT for Period 1 Day 1 the following day.

9.5.3 Vital Signs

For each patient, vital signs measurements should be conducted according to the Schedule of Activities (Section 2).

Blood pressure and pulse rate should be measured after at least 10 minutes supine at screening and semi-recumbent supine on Day 1.

9.5.8 Treatment of Hyperglycemia and Hypoglycemia

Patients will be without food intake from the start of the MMTT to completion of blood collection (approximately 420 minutes) unless required to treat hypoglycemia (see Section 9.5.6.2 for definition of hypoglycemia) with either rapidly absorbable oral carbohydrates or IV glucose.

Patients may consume up to 20 g of carbohydrates to treat or prevent hypoglycemia (Level 2 \leq 54 mg/dL [see Section 9.5.6.2] during the fasting periods (See Sections 2, 6.3.1, and

[9.2.2](#)). If carbohydrates are administered and consumed, this must be captured in the patient's diary and eCRF.

11 References

AMIS database. 13 June 2006. DIMDI (Deutsches Institut für medizinische Dokumentation und Information). Available at: <https://www.dimdi.de/dynamic/de/db/recherche/index.htm>. Accessed: November 07, 2017.

Chow SC & Liu JP. Design and analysis of bioavailability and bioequivalence studies. 3rd ed. Florida: Taylor and Francis Group, LLC; 2009:88-90

Humalog [package insert]. Indianapolis, IN: Eli Lilly and Company; 2015.

Remodulin [package insert]. Research Triangle Park, NC: United Therapeutics Corp; 2014.

Appendix 6. Revised Protocol Sections

6.1. Inclusion Criteria

Patients are eligible for inclusion in the study only if they meet all of the following criteria at screening and/or enrollment:

- [1] are male or female patients with T1₂DM for at least 1 year. A diagnosis of T1₂DM is based on medical history with a fasting C-peptide <0.30 nmol/L.

2. ABBREVIATIONS

Abbreviations pertain to the Statistical Analysis Plan (SAP) only (not the tables, figures and listings [TFLs]).

AE	Adverse event
ALP	Alkaline phosphatase
ALT	Alanine aminotransferase
AUC	Area under the concentration versus time curve
AUC(0-15min)	Area under the concentration versus time curve from time zero to time 15 minutes
AUC(0-30min)	Area under the concentration versus time curve from time zero to time 30 minutes
AUC(0-1 h)	Area under the concentration versus time curve from time zero to time 1 hour
AUC(0-2 h)	Area under the concentration versus time curve from time zero to time 2 hours
AUC(0-7 h)	Area under the concentration versus time curve from time zero to time 7 hours
AUC(3-7 h)	Area under the concentration versus time curve from time 3 hours to time 7 hours
AUC(0-∞)	Area under the concentration versus time curve from time zero to infinity
C _{max}	Maximum observed drug concentration
CI	Confidence interval
CRF	Case Report Form
CSR	Clinical Study Report
CRU	Clinical Research Unit
CV	Coefficient of variation
Early 50% t _{max}	Time to early half-maximal drug concentration
EC	Early Clinical
ECG	Electrocardiogram
ED	Early discontinuation
e.g.	For example (Latin: exempli gratia)
GD	Glucodynamic

ICH	International Council on Harmonisation
Late 50% t_{\max}	Time to late half-maximal drug concentration
LSmeans	Least square means
MedDRA	Medical Dictionary for Regulatory Activities
MRE	Magnetic resonance elastography
MMTT	Mixed meal tolerance test
PG	Plasma glucose
PK	Pharmacokinetic
SAP	Statistical Analysis Plan
SC	Subcutaneous
SD	Standard deviation
SMPG	Self monitored plasma glucose
TBL	Total bilirubin
T1DM	Type 1 diabetes mellitus
TFLs	Tables, Figures, and Listings
t_{\max}	Time of maximum observed drug concentration
ULN	Upper limit of normal
WHO	World Health Organization

3. INTRODUCTION

This SAP has been developed after review of the Clinical Study Protocol (final version dated 10 August 2017), amendment (a) (dated 10 October 2017) and SAP version 1 (dated 09 November 2017).

This SAP describes the planned analysis of the safety, tolerability, pharmacokinetic (PK) and glucodynamic (GD) data from this study. A detailed description of the planned TFLs to be presented in the clinical study report (CSR) is provided in the accompanying TFL shell document.

The intent of this document is to provide guidance for the statistical, GD and PK analyses of data. In general, the analyses are based on information from the protocol, unless they have been modified by agreement between Eli Lilly and Company and CCI [REDACTED]. A limited amount of information concerning this study (e.g., objectives, study design) is given to help the reader's interpretation. This SAP must be signed off prior to first subject administration for this study. When the SAP and TFL shells are agreed upon and finalized, they will serve as the template for this study's CSR.

This SAP supersedes the statistical considerations identified in the protocol; where considerations are substantially different, they will be so identified. If additional analyses are required to supplement the planned analyses described in this SAP, they may be performed and will be identified in the CSR. Any substantial deviations from this SAP will be agreed upon between Eli Lilly and Company and Covance EC Biometrics and identified in the CSR. Any minor deviations from the TFLs may not be documented in the CSR.

This SAP is written with consideration of the recommendations outlined in the International Council on Harmonisation (ICH) E9 Guideline entitled Guidance for Industry: Statistical Principles for Clinical Trials¹ and the ICH E3 Guideline entitled Guidance for Industry: Structure and Content of Clinical Study Reports².

4. STUDY OBJECTIVES

4.1 Primary Objective

- To evaluate the PK of insulin lispro following a single subcutaneous (SC) injection of LY900014 and Humalog in patients with type 1 diabetes mellitus (T1DM).

4.2 Secondary Objectives

[figure not shown]
- To evaluate the effect of injection-to-meal timings (immediately before the start of meal, and 20 minutes following the start of the meal) on the GD response to LY900014 compared to Humalog, as measured by the mixed meal tolerance test (MMTT).
- To evaluate the tolerability of LY900014.

4.3 Exploratory Objective

- Explore the formation of anti-drug antibodies to insulin lispro.

5. STUDY DESIGN

This is a Phase 1, patient- and investigator-blind, randomized, 2-treatment, 4-period crossover study in patients with T1DM to evaluate the insulin lispro PK and GD characteristics of LY900014 compared to Humalog following single SC injections administered at 2 different injection-to-mealtime intervals; either immediately before or 20 minutes following the start of the test meal. This study may be conducted at 1 or more clinical research units (CRUs).

Treatment	LY900014 or Humalog	Dose Timing Relative to Meal (minute)*
A	LY900014	0
B	LY900014	+20
C	Humalog	0
D	Humalog	+20

* Time 0 is immediately before test meal

Abbreviations: ED = early discontinuation; T1DM = type 1 diabetes mellitus

Figure 1. Illustration of study design

Patients will be required to attend the CRU on at least 8 occasions (no more than 10 occasions if dose-finding and/or one MMTT rescheduled) as noted in the Study Schedule (see Section 2 of protocol):

- Informed consent
- Screening visit
- Lead-in and insulin transition period (see Section 9.2.1 of the protocol)
- 4 inpatient CRU study visits (including dose finding assessment [see Section 9.2.2 of the protocol])
- A follow-up visit

Eligible patients who have satisfied the entry criteria and completed all screening procedures will return to the CRU at least 2 weeks prior to Period 1 Day -2 to begin a lead-in and insulin transition period. When patients visit the CRU to begin the lead-in period, patients will receive instruction on general diabetes education including measurement of self-monitored plasma glucose (SMPG) and receive instruction on the insulin transition (see Section 9.2.1 of the protocol). During the insulin transition period, patients will transition from their current basal insulin therapy to site provided insulin glargine and Humalog CCI (see Section 9.2.1 of the protocol). Following insulin transition, patients will return to the CRU for the dose-finding assessment (see Section 9.2.2 of the protocol) on either the evening of Day -2, Period 1 or early morning of Day -1, Period 1. The dose-finding assessment will use Humalog administered immediately before a standardized liquid test meal to inform the dose of LY900014 and Humalog to be used during subsequent study MMTT assessments. Upon completion of the dose-finding assessment, patients will be randomised to 1 of 4 treatment sequences. Prior to the MMTT in each study period, patients will undergo a run-in period (see Section 9.2.3.1 of the protocol) to achieve a predetermined glucose target of 135 ± 15 mg/dL (7.5 ± 0.8 mmol/L). Once the glucose target has been attained, patients will proceed with the MMTT in which a single individualized SC dose of LY900014 or Humalog will be administered either immediately before the test meal or 20 minutes following the start of the test meal (see Section 9.2.3.2 of the protocol).

Doses of LY900014 and Humalog during the 4 study periods will be separated by a minimum washout of approximately 21 hours. The maximum duration allowed for all 4 periods is approximately 6 weeks. Patients will continue using site-provided Humalog and insulin glargine during the washout periods between MMTTs (see Section 7.7 for use of concomitant medication and basal insulin). During the washout periods, patients will be instructed to perform regular blood glucose monitoring (see Section 9.5.7 of the protocol).

Following completion of all study procedures in each Period, patients may be offered a meal and discharged from the CRU at the discretion of the principal investigator.

Study governance considerations are described in detail in Appendix 3 of the protocol.

6. TREATMENTS

The following is a list of the study treatment abbreviations that will be used in the TFLs.

Study Treatment Name	Treatment order in TFL
LY900014 (0 min)	1
LY900014 (+ 20 min)	2
Humalog (0 min)	3
Humalog (+ 20 min)	4

7. SAMPLE SIZE JUSTIFICATION

An initial 36 patients may be enrolled in order that approximately 30 patients complete the study. Thirty completing patients will provide greater than 95% power to demonstrate a 2-fold increase in the serum insulin lispro area under the concentration versus time curve from time zero to 30 minutes [AUC(0-30min)] between LY900014 and the Humalog. Testing will be done at an alpha level of 0.05 with a 2-sided confidence interval (CI). The sample size will also provide greater than 95% power to demonstrate a 35% reduction of early 50% time to maximum observed drug concentration (early 50% t_{max}). The estimated standard deviation (SD) of within-subject difference on the log scale is 0.35 for AUC(0-30min) and 0.25 for early 50% t_{max} , according to an analysis of internal Lilly data (CCI) for LY900014 and Humalog administered in a repeat-dose study.

With this sample size, there is approximately 80% power to detect a -30 mg·h/dL difference (LY900014 versus Humalog when both are given immediately before meals) in postprandial glucose Δ AUC[0-2h]. This is based on an analysis of ITRG which showed a SD of within-patient difference of 56.20 mg·h/dL on the original data scale.

Patients who are randomized but drop out before completing assigned treatment may be replaced to ensure that approximately 30 patients complete the study.

8. DEFINITION OF ANALYSIS POPULATIONS

The “Safety” population will consist of all patients who received at least one dose of study drug, regardless of whether or not they completed all protocol requirements.

Primary statistical analyses of PK parameters will be conducted on the set of patients who have evaluable PK data from at least one period where LY900014 is dosed and at least one period where Humalog is dosed. The insulin lispro PK is not influenced by the injection-to-meal timing of dosing.

For the analyses of GD parameters, patients with evaluable GD data for both treatments (LY900014 and Humalog) within each injection-to-meal timing (immediately before the start of meal or 20 minutes after the start of the meal) will be included. If data for only one treatment (LY900014 or Humalog) exists for an injection-to-meal timing, that data will not be included in the analysis.

Supportive analyses will be conducted on the set of patients who complete all treatment periods. A completer is defined as a patient with data for all 4 combinations of treatment and injection-to-meal timing.

All protocol deviations that occur during the study will be considered for their severity/impact and will be taken into consideration when subjects are assigned to analysis populations.

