randomised to 1 of 4 treatment sequences according to the actual randomization table provided to the site. In each study period, patients will undergo an MMTT. Each patient will receive a single subcutaneous injection of either LY900014 or Humalog either immediately before the test meal or 20 minutes following the start of the test meal. All treatment procedures will be inpatient stays of approximately 2 days per period and require a maximum of 6 weeks to complete 4 periods. Each study dosing will be separated by a minimum of 21 hours and may occur on consecutive visits, however patient inclusion is subject to required screening criteria. The follow-up or early discontinuation visit should occur at least 14 days after the last dose of the study drug.

Treatment:

LY900014: Single individualized SC dose per assessment period

Humalog: Single individualized SC dose per assessment period

Number of Patients:

Up to 36 patients may be enrolled to ensure that at least 30 patients will complete the study. Thirty completing patients will provide greater than 95% power to demonstrate a 2-fold increase in the serum insulin lispro AUC(0-30min) between LY900014 and Humalog when both are given immediately before meals.

Statistical Analysis:

Primary statistical analyses of PK and GD parameters will be conducted on the set of patients who complete all treatment periods. Supportive analyses may be done on the key parameters for the patients who complete at least the first period of treatment. Safety analyses will be conducted on the set of patients receiving at least 1 dose of the study drug to which they are randomized, regardless of whether or not they completed all protocol requirements.

Unless otherwise noted, all tests of treatment effects will be conducted at a 2-sided alpha level of 0.05, and confidence intervals (CIs) will be calculated at 95%, 2-sided.

Safety: All investigational product and protocol procedure AEs will be listed, and if the frequency of events allows, safety data will be summarized using descriptive methodology. Safety parameters will be listed and summarized using standard descriptive statistics.

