10.1. Sample Size Determination

An initial 36 patients may be enrolled in order that approximately 30 patients complete the study. Thirty completing patients will provide greater than 95% power to demonstrate a 2-fold increase in the serum insulin lispro AUC(0-30min) between LY900014 and the Humalog. Testing will be done at an alpha level of 0.05 with a 2-sided confidence interval (CI). The sample size will also provide greater than 95% power to demonstrate a 35% reduction of early 50% t_{max} . The estimated standard deviation of within-subject difference on the log scale is 0.35 for AUC(0-30min) and 0.25 for early 50% t_{max} , according to an analysis of internal Lilly data (Study I8B-FW-ITRG [ITRG]) for LY900014 and Humalog administered in a repeat-dose study.

With this sample size, there is approximately 80% power to detect a -30 mg·h/dL difference (LY900014 versus Humalog when both are given immediately before meals) in postprandial glucose Δ AUC[0-2h]. This is based on an analysis of ITRG which showed a standard deviation of within-patient difference of 56.20 mg·h/dL on the original data scale.

Patients who are randomized but drop out before completing assigned treatment may be replaced to ensure that approximately 30 patients complete the study.

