9.3.2 Pharmacokinetic Statistical Inference

Patients who did not keep identical insulin lispro doses for both treatments (LY900014 and Humalog) will be excluded from the statistical analysis of the PK parameters.

Log-transformed AUCs and C_{max} for insulin lispro will be evaluated to estimate geometric means, ratios of geometric means of insulin lispro within LY900014 to Humalog, and their corresponding 95% CIs of the ratios using the mixed-effects model that includes treatment (LY900014, Humalog) and period as fixed effects and patient as a random effect.

Example SAS code:

```
proc mixed data=pk;  
class patient period treatment;
```

```
model logpk = treatment period / ddfm=kr alpha=0.05;  
random patient;  
lsmeans treatment;  
run;
```

For AUC(0-∞), the analysis above will be used to produce an assessment of within-patient and between-patient variability for each treatment.

The same model without log transformation will be used for the analysis of the PK time parameters (early 50% t_{max} , late 50% t_{max} , and t_{max}). Least-squares means (LSmeans), treatment differences in LSmeans, and the corresponding 95% CIs for the treatment differences will be estimated from the model. The p-value on the difference between LSmeans will be used to determine statistical significance. The treatment ratios and 95% CIs for the ratios will be calculated using Fieller's theorem (Chow and Liu 2009).

Statistical significance will be achieved when the p-value for a test is less than 0.05.

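### The primary PK model omits the randomised injection-to-meal timing on an untested assertion of no effect; the pooled ratio stays valid with complete data, but timing and its interaction should be modelled and reported.

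*SAP*

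**What the plan says.** - **Design.** Protocol 5.1 and SAP 5 define four conditions: LY900014 at 0 and +20 minutes, and Humalog at 0 and +20 minutes. Under SAP 5, "patients will be randomised to 1 of 4 treatment sequences". SAP 6 lists the four conditions as separate labels for the tables, figures and listings.
- **PK model.** SAP 9.3.2 specifies a "mixed-effects model that includes treatment (LY900014, Humalog) and period as fixed effects and patient as a random effect", and protocol 10.3.2.2 gives the same terms. The example code has no timing term. SAP 9.3.2 also uses this analysis to describe within- and between-patient variability of AUC(0-∞) for each treatment.
- **GD model.** SAP 9.4.2 includes timing and the treatment-by-timing interaction.
- **Reason given.** SAP 8 says: "The insulin lispro PK is not influenced by the injection-to-meal timing of dosing". It cites no source, and no planned analysis examines it.
- **PK set.** Protocol 10.3 makes patients who complete all periods the primary set. SAP 8 instead admits any patient with one evaluable LY900014 period and one evaluable Humalog period, and does not require the timings to match. For GD, SAP 8 does require both treatments within a timing.
- **Power.** The protocol synopsis claims "power to demonstrate a 2-fold increase in the serum insulin lispro AUC(0-30min) between LY900014 and Humalog when both are given immediately before meals". Protocol 10.1 speaks only of a "2-fold increase in the serum insulin lispro AUC(0-30min) between LY900014 and the Humalog", and SAP 7 likewise names no timing for PK. Both keep the before-meal restriction for glucose ΔAUC(0-2h) only.

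**The concern.** Timing is a randomised factor, so leaving it out of the primary model needs either evidence or a check. The plan offers neither, although this design could supply the check: the same patients are injected just before, and 20 minutes into, a liquid meal with about 100 g of carbohydrate.

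Three things are at stake. First, the synopsis names a before-meal contrast that the PK model does not estimate. Second, any timing effect is counted as residual error, and as within-patient variability of AUC(0-∞), because a patient's two profiles on one insulin are true replicates only if timing does nothing. Third, the wider SAP 8 set lets a timing effect into the treatment contrast for patients whose two insulins were given at different timings. A smaller matter is interpretation. Secondary objective 1 concerns timing and glucose, and a modelled PK comparison by timing would help to separate an absorption effect from meal matching.

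**Working it through.** **Inputs.** From protocol 10.1 and SAP 7: 30 completers, two-sided alpha 0.05, and SD of the within-subject log difference 0.35 for AUC(0-30min) and 0.25 for early 50% t_max. Target effects are a ratio of 2.0 and a 35% reduction. For GD: a difference of -30 mg·h/dL with SD 56.20. The documents give no size for a timing effect or an interaction, so all such values below are assumptions.

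**1. The plan's own figures (paired t, 29 df).**
- AUC(0-30min): SE = 0.35/√30 = 0.064. The target ln 2 = 0.693 is about 10.8 SEs, so power exceeds 99.9%. The plan states more than 95%.
- Early 50% t_max: power also exceeds 99.9%.
- GD: SE = 56.20/√30 = 10.26 and 30/10.26 = 2.92, giving 80.7% power. The plan states about 80%.

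All three reproduce. The AUC calculation is also the before-meal contrast on its own, whose 95% CI factor is exp(2.045 × 0.064) = 1.14 in each direction.

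**2. Precision of the other contrasts.** Per-profile residual variance is 0.35²/2 = 0.06125 (SD 0.247), assuming equal variances.
- Pooled contrast: SE = 0.247 × √(1/60 + 1/60) = 0.045.
- Interaction (ratio of ratios): SE = √(4 × 0.06125/30) = 0.090, a CI factor of about 1.20.
- Power of the interaction test: about 21%, 68% and 88% for a ratio of ratios of 0.90, 0.80 and 0.75.

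**3. Timing effect d common to both products, complete data.** Each insulin is given once at each timing, so d cancels from the treatment difference. What remains is a sum of squares of 120 × d²/4 = 30d² in the residual, which has 120 − 1 − 29 − 3 − 1 = 86 df. Relative inflation of the residual variance is (30d²/86)/0.06125:
- d = 0.1: about 6%
- d = 0.2: about 23%
- d = 0.3: about 51%

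At d = 0.3 the pooled SE becomes 0.045 × √1.51 = 0.056. A simulation of 200 trials with true ratio 2.0 and a timing effect of −0.3 gave a pooled ratio of 2.00 and an SE of 0.056.

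**4. Interaction, complete data.** The pooled ratio is the geometric mean of the two timing-specific ratios. With a before-meal ratio of 2.0:
- +20-minute ratio 1.8: √(2.0 × 1.8) = 1.90
- 1.5: 1.73
- 1.2: 1.55
- 1.0: 1.41

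Simulation of the second case (ratio of ratios 0.75) gave 1.74 from the planned model. The model with timing and interaction gave 2.02 for the before-meal ratio.

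**5. Mismatched timings.** Suppose 6 of 30 patients contribute only LY900014 at 0 and Humalog at +20, with d = −0.3 and no interaction. Ignoring period, a complete patient carries weight 1 and a two-profile patient 0.5, so the shift is (6 × 0.5 × 0.3)/(24 + 3) = 0.033 log, or 2.00 × e^0.033 = 2.07. Simulation with period in the model gave 2.06. The model with timing and interaction gave 1.99 for the before-meal ratio, with SE 0.070.

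**The case against.** The best defence is that pooling answers the stated question. The primary objective names no timing, timing appears only in the GD objective, and PK sampling times run from the injection, not the meal. The two-level model was already in the protocol without the SAP 8 sentence, so that sentence is not shown to be the reason for pooling. Only the synopsis attaches a before-meal condition to PK power. Protocol 10.1 and SAP 7 do not, and the SAP says that it takes precedence over the protocol's statistical considerations. SAP 8 also commits to a supportive analysis of patients with all four conditions, which excludes mismatched patients, and dropouts may be replaced. Even the inflated pooled SE of 0.056 is below the 0.064 of the before-meal contrast.

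Most of this stands, and it is why the pooled average should remain primary. Three points survive it. The assertion is unsupported and untested. The completer analysis has no timing term, so it cannot test the assertion or remove timing from the error. The synopsis still disagrees with the body of the plan.

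A reader might infer more than the documents support:
- *That any effect of the meal on absorption makes the primary ratio a mixture true of neither timing.* That needs an interaction; a shared effect cancels when data are complete. The documents give no reason to expect an interaction.
- *That PK will never be seen by timing.* The four output labels in SAP 6 allow descriptive summaries by condition. What is missing is a modelled comparison.

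**Conclusion.** The point holds as a gap in the model and an inconsistency between sections. It does not show that the primary result would be wrong. With complete data the pooled LY900014/Humalog ratio is a valid equal-weight average over timings. It differs from the before-meal ratio only under a treatment-by-timing interaction (for example 1.73 against 2.0 if the +20-minute ratio were 1.5), or slightly through mismatched patients (2.06 against 2.00 in the adverse case above). A shared timing effect of 0.1 to 0.3 log would raise residual variance by about 6% to 51%, and within-patient variability would be overstated for the same reason.

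It would be wrong to conclude that the trial is underpowered for the before-meal comparison: that contrast alone has more than 99.9% power for a 2-fold ratio.

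The timing effects and interactions are assumed, since the documents give none. The inflation figures use the AUC(0-30min) SD; no SD is given for AUC(0-∞), so the size of the overstatement there is unknown.

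**What to change.** 1. In SAP 9.3.2 and protocol 10.3.2.2, fit the PK parameters with treatment, timing, treatment-by-timing and period as fixed effects and patient as random, as already done for GD. Use the same model in the supportive completer analysis.
2. Name the LY900014/Humalog contrast averaged equally over the two timings as the primary result, in line with the primary objective. Taken from this model, it is also protected against a shared timing effect when periods are missing.
3. Report the 0-minute contrast, the +20-minute contrast and the interaction estimate with its 95% CI as supportive.
4. Replace the SAP 8 sentence on timing with that commitment.
5. Align the synopsis power wording for AUC(0-30min) with protocol 10.1 and SAP 7.

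The cost is two residual degrees of freedom (86 to 84), a few lines of text and code, and a few extra output lines; no new data are needed. The interaction CI of about ×/÷ 1.20 will not exclude modest effects, so the SAP should add that a non-significant interaction test is not proof that timing has no effect.
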